2 INTRODUCTION

Daily disposable (DD) contact lenses are popular choices today and are frequently recommended by eye care professionals, as this avoids the use of a lens cleaning product and with the goal to reduce symptoms of dryness and discomfort.¹ As a result, DD lenses account for 45% of all soft lens fits today.²

DD lenses were mainly available in hydrogel materials in the past, however, more and more new high oxygen-permeable silicone hydrogel (SiHy) DD lenses are becoming available today.

The goal of this study is to compare the performance of MyDay Energys, a SiHy DD lens from CooperVision Inc., which has successfully been established on the market, with ACUVUE OASYS MAX 1-Day, a DD SiHy lens recently launched by Johnson & Johnson Inc.

3 OBJECTIVES

To evaluate and compare the performance of MyDay Energys (CONTROL) (CooperVision Inc.) and ACUVUE OASYS MAX 1-Day sphere (TEST) (Johnson & Johnson Inc.) in existing soft lens (CL) wearers over one week of wear.

The primary outcome variable for this study is:

Lens handling on removal collected on Day 6 on the at-home ratings (0-100 scale).

4 HYPOTHESIS

The null hypothesis is that there will be no difference for lens handling on removal on Day 6 (Athome ratings, 0-100 scale) between CONTROL compared to TEST lens.

5 MATERIALS AND METHODS

5.1 STUDY DESIGN

5.1.1 OVERALL DESIGN

This study is a prospective, bilateral eye, double-masked, randomized, 1-week cross-over, dailywear design involving two different daily disposable lens types. Each lens type will be worn for approximately one week, during which participants record their subjective lens-wear experience on three different days.

5.1.2 RANDOMIZATION

A randomization schedule will determine the order of CONTROL and TEST CL wear for the first/second week for each participant. Participants will be randomized immediately prior to their first lens dispense.

This randomization schedule will be generated for each site using a web-based program: (for example www.randomization.com). The lens type that will be worn during the first week is called "Lens type #1", the lens type dispensed for the second week is called "Lens type #2". The final study randomization schedule will be generated by CORE's Database Administrator and provided to the unmasked research assistants at each site.

5.1.3 MASKING

This study will be double masked i.e. participants and investigators will be masked to the lens type dispensed. In order to achieve this, unmasked research assistants will determine the lens order according to the randomization schedule (see section 5.1.2) and will over-label the lens packages/foils prior to dispense by placing strongly adhesive stickers on the packages/foils to mask the participant and investigator to the lens brand. At the fitting visit both lens types will be fit, but only the participant can be masked to the lens type during this process because the investigator needs to know which type is being fit in order to follow the fitting guide when making changes to the lens. During the lens wear phases both investigators and participants will be masked.

5.2 INVESTIGATIONAL SITES

5.2.1 NUMBER OF SITES

This study will be conducted at approximately 4 optometry practice sites in the USA.

5.2.2 INVESTIGATOR RECRUITMENT

The principal investigator at each site will undergo qualification by CooperVision oversight personnel and among other requirements they will be required to fulfil the following criteria:

- Is a licensed eye care professional with at least two years of contact lens fitting experience.
- Can demonstrate training in Good Clinical Practice (GCP) by the already trained principal investigator.
- Accepts responsibility for the conduct of the study at their site.

EX-MKTG-148 SUN Protocol v1.5 23Feb2023

- Has in-office email and document scanning capabilities.
- Will scan and send all study visit documents to CORE, ideally the same day* as the visit or at most within 2 days of the study visit.
- Is willing to follow the study protocol and to co-operate with the study monitors at CORE.

* Study documents are required as soon as possible because this allows a timely data review, query and entry.

5.3 STUDY POPULATION

5.3.1 SAMPLE SIZE CALCULATION

The sample size calculation was based on "lens handling at removal" using historical data at 1 week in which participants used a 0-100 scale (100 being best).

A sample size of 64 is required to detect a mean difference in "handling at removal" of 10 units on a 0 to 100 scale using a standard deviation of the paired differences of 24.2 with 90% power and alpha 0.05 in a two-tailed t-test. Therefore, up to 73 participants will be dispensed with study products with the goal to complete at least 64.

Power and Sample Size (handling on removal (0-100)

Paired t Test
Testing mean paired difference = 0 (versus ≠ 0)
Calculating power for mean paired difference = difference
α = 0.05 Assumed standard deviation of paired differences = 24.2

Results

Difference	Sample Size	Target Power	Actual Power
10	48	0.80	0.800662
10	54	0.84	0.846406
10	64	0.90	0.902344

Figure 1: Sample size calculation graph

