12 STATISTICAL ANALYSIS AND DATA MANAGEMENT

12.1 STATISTICAL ANALYSIS

All data will be analyzed by CORE at the University of Waterloo. Unmasked data analysis will be conducted using Statistica 10, Statsoft or other suitable software. Descriptive statistics will be provided on demographic data (age, gender, refractive error distribution, etc.). Table 7 lists the primary and other outcome variables and anticipated statistical procedures.

Visual acuity results will be converted to LogMAR for analysis purposes.

Comparisons will be made between the study lenses for the variables measured at the 1-week visits. Additionally the subjective ratings completed on days 1, 3 and 6 with each study lens will be compared for differences and equivalence. A binomial test will be used to analyze the results for the count data of subjective preferences and experience responses. Where relevant, the number of "no preference" responses will be evenly distributed to the two options on the basis they would be equally likely to choose either.

For assessments conducted for each eye separately, the right eye will be used for analysis. If a general difference is found (paired t-test / Wilcoxon matched pairs) between OD and OS, a comment will be provided

Where appropriate, data may be presented as both mean and as counts by 'bucket' groups.

Additional analysis may be conducted

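### Does sizing the cross-over with a plain paired t-test show that the primary analysis wrongly leaves out a period term?

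*Combined protocol and SAP*

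**What the plan says.** The primary outcome is "Lens handling on removal collected on Day 6 on the at-home ratings (0-100 scale"), given in section 3. Section 5.1.1 describes a "randomized, 1-week cross-over, dailywear design involving two different daily disposable lens types". On lens order, section 5.1.2 says: "A randomization schedule will determine the order of CONTROL and TEST CL wear for the first/second week for each participant". The same section adds: "This randomization schedule will be generated for each site using a web-based program". It states neither an allocation ratio nor block sizes. Section 5.2.1 plans about four sites.

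The sample size in section 5.3.1 rests on a 10-unit mean paired difference, "using a standard deviation of the paired differences of 24.2 with 90% power and alpha 0.05 in a two-tailed t-test". The result is 64 completers, with a printed power of 0.902344.

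On the analysis itself, section 12.1 says: "Table 7 lists the primary and other outcome variables and anticipated statistical procedures". That table is not in the public text. The visible part of section 12.1 announces comparisons between the lenses and names no test for the primary outcome. It does name the paired t-test and the Wilcoxon test, but only for the check of right eye against left eye.

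**The concern.** In a two-period cross-over, ratings can drift from the first week to the second whichever lens is worn. That drift enters the TEST minus CONTROL difference with one sign in participants who wear TEST first and with the opposite sign in the others. A plain paired t-test counts the drift as noise. If the two sequences differ in size, it also moves the estimated lens difference.

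The only test visible in connection with the primary outcome is the paired t-test used for sizing. Read as the analysis plan, it suggests that the trial will use an interval wider than necessary, have less than its stated 90% power, and be exposed to a chance imbalance in lens order. A period term would cost one degree of freedom and one line of text.

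**Working it through.** **Inputs.** From section 5.3.1: difference 10, SD of paired differences 24.2, two-sided alpha 0.05, N=64. Assumed, because the documents do not give them: the period effect π (shown at 3, 5, 10 and 15 units) and the split between sequences (n1/n2).

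**1. The plan's own figure.** Paired t-test, standard error 24.2/√64 = 3.025, noncentrality 10/3.025 = 3.306, 63 degrees of freedom. The noncentral t distribution gives power 0.9023, as printed. The printed figures for N=48 (0.8007) and N=54 (0.8464) also reproduce.

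**2. The same design with a period term.** The lens effect is the mean of the two sequence means, with standard error (24.2/2)·√(1/n1 + 1/n2). At 32/32 this is 12.1 × 0.25 = 3.025, the same as before, with 62 degrees of freedom. Power is 0.9022 at N=64 and 0.8975 at N=63, so 64 is again the smallest N for 90%. The sizing statement therefore cannot tell the two analyses apart.

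**3. What an unadjusted analysis would lose, if it were planned.** Model: d = τ ± π + e, with the sign set by sequence and e having SD 24.2. The sample mean is normal with mean τ + π(n1−n2)/N. The sum of squares divided by 24.2² is noncentral chi-square with 63 degrees of freedom and noncentrality π²(N − (n1−n2)²/N)/24.2². The 95% half-width at 32/32 is about 1.998·√(24.2² + π²·64/63)/8; for π=10 this is 1.998 × 26.215/8 = 6.55. The adjusted analysis gives 1.999 × 24.2/8 = 6.05 and 90.2% power.

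| Assumed π, 32/32 | Unadjusted power | Type I error | Half-width |
|---|---|---|---|
| 3 | 90.0% | 4.8% | 6.09 |
| 5 | 89.5% | 4.5% | 6.17 |
| 10 | 87.1% | 3.4% | 6.55 |
| 15 | 82.6% | 2.1% | 7.13 |

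With equal sequences the unadjusted test is unbiased and conservative. At 5 units the loss is 0.7 points of power and a 2% wider interval.

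**4. If 24.2 already contains period variation.** Section 5.3.1 calls it an SD of paired differences from historical data and does not state the design behind those data. If they came from a cross-over analysed without a period term, the residual SD is √(24.2² − π²·64/63), which is 23.67 for π=5 and 22.00 for π=10. Unadjusted power at 32/32 is then 90.7% and 92.2%, so there is no shortfall against 90%. Adjusted power would be 91.4% and 94.7%.

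**5. Where adjustment costs power.** Under simple unblocked allocation, averaged over Binomial(64, 0.5) splits, adjusted power is 89.75%. Unadjusted power is 90.2% at π=0, 89.8% at π=3, 89.0% at π=5 and 85.3% at π=10. Below about 3 units adjustment loses on average. With no period effect, adjusted power at a 40/24 split is 88.3%, about 2 points below 90.2%.

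**The case for a change.** The best case for raising the point is that adjustment is nearly free and that the protocol does not say the schedule is blocked. Without blocking, a split of 36/28 or worse has probability 2 × P(Bin(64, 0.5) ≤ 28) = 38%. At 36/28, a 10-unit period effect shifts the unadjusted estimate by 10 × 8/64 = 1.25 units. Power is then 77% or 94% depending on direction, against 89.8% adjusted. At a realised 40/24 split with the same period effect, the unadjusted type I error is 9.9%, so for unequal sequences more than efficiency would be at stake.

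These figures are correct, and as general advice on cross-over trials the argument is sound. What it lacks is a statement in this plan to which it applies. No section says that the primary comparison will be unadjusted, and the place where the procedure is set out cannot be seen. The unfavourable figures need both a period effect as large as the lens difference being sought and a clear imbalance. Nothing in the documents points to such an effect: participants are habitual soft lens wearers of at least three months (section 5.3.3), and both ratings are taken on Day 6 of their week. If the per-site schedules at about four sites are blocked (block sizes 2 to 8 assumed), a split of 36/28 or worse has a probability of 0.3% or less.

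**Conclusion.** No defect is shown. Section 5.3.1 is a sizing statement, its figures reproduce, and its N of 64 is right for either analysis when the sequences are about equal. Whether the primary analysis has a period term is a matter for Table 7. That table is absent from the public text, which says nothing against the plan.

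The possible gain rests wholly on an assumed period effect. It is 0.7 points of power at 5 units with equal sequences and 3.1 points (90.2 − 87.1) at 10 units. Measured against the planned 90% it is no shortfall at all if 24.2 already includes period variation, and it turns into a small loss below about 3 units under unblocked allocation. What remains is a reasonable preference between two valid analyses. These results assume normally distributed differences, 64 completers and, except where stated, 24.2 as the SD within sequence.

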5.3.2 NUMBER OF PARTICIPANTS

Participants will be recruited using site records, databases and advertising materials (eg. posters, email scripts) approved by the ethics review board. All initial individual-targeted recruitment activities, such as any direct mailing of recruitment scripts, will be conducted by practice staff that are not directly involved in conducting the research. This separation will reduce any undue influence of the optometrist-patient relationship. This process will also eliminate opportunity for the investigator to access personal health information before any consent for disclosure is provided by the potential participant.

It is anticipated that up to 73 potential participants may attend a Screening visit and up to 70 participants may be randomized and dispensed with study products, with a target of at least 64 completing the study.

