5.5.1 VISIT 0 SCREENING & FITTING VISIT

Informed consent shall be obtained in writing from the participant and the process shall be documented before any procedure specific to the clinical investigation is carried out.

Participants will be assigned a unique alpha-numeric study ID after they sign the consent documentation i.e. before their eligibility for the study has been confirmed. Each site will use a different letter preceding the participant ID number. For example, participant 01 at site T will be T01, and participant 01 at site N will be N01. Ineligible participants will be discontinued from the study.

The investigator will determine participant eligibility using the inclusion and exclusion criteria. The study procedures are outlined below:

1. The participant is expected to insert their habitual contact lenses at least 2 hours before attending the visit.

- 2. The participant will be required to read and sign an Informed Consent Form prior to enrollment. When the participant has signed the consent form, the participant will be considered enrolled in the study and will be assigned a study ID.
- 3. Participant demographics and medical history (age, sex, medical conditions, medications, allergies).
- 4. Contact lens history (habitual lens information and wearing habits).

5.		l
6.		
7.	The participant removes their habitual contact lenses.	
8.		
9.		
10.		

- 11. After a minimum 5-minute washout time after fluorescein insertion, the participant will be fit with the study lenses.
- 12. The investigator will fit both study lenses (CONTROL and TEST) using the pre-ordered or provided lenses following the manufacturers fitting guidelines.

Trial fitting of both study lenses:

- a. The contact lens power will be chosen based on the vertex-corrected spectacle refraction.
- b. The contact lenses will be provided to participants in a manner that does not unmask the participant as described in Section 5.1.3.
- c. The participant will insert the lenses, allow to settle for at least 10 minutes.
- d.
 e.
- f. If any changes are made to the lens power, the above procedures (b to e) will be repeated.
- 13. The investigator will confirm that the participant meets the eligibility specifications set out in the inclusion criteria and exclusion criteria and is eligible to continue in the study.

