14 STUDY MONITORING

Each site will provide regular status reports to CORE. Status reports will include:

- The number of participants screened, enrolled, and randomized (i.e. assigned a study ID number), discontinued and completed.
- Details of all protocol deviations, adverse events, device malfunctions.
- Reports of unintended events.

CORE will collate the site updates and provide 2-weekly status reports to the study sponsor.

Study monitoring visits to the sites may be conducted by CORE, the sponsor, or sponsor's designate, throughout the study and will be scheduled in conjunction with the Principal Investigator at each site. In addition study records may be inspected by the sponsor, the sponsor's designate, Sterling Institutional Review Board, and by regulatory authorities in Canada and the United States, namely Health Canada and the United States Food and Drug Administration (FDA); however, they will not be permitted to take away any records containing identifiable personal information.

Study data review and data monitoring will be conducted by CORE personnel. To improve data integrity, data entry will be conducted by one person and a second person will visually compare the data entry to the source documents. Data queries will be reported to the site within 5 working days of receipt of initial data. A response resolving the query will be expected from the site within 5 working days of receipt of the query.

All adverse events and protocol deviations will be reviewed by the site Principal Investigator and CORE's Lead Coordinator. All serious adverse events and major protocol deviations will be reviewed by the site Principal Investigator and CORE's Director and/or Head of Clinical Research.

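### Sections 5.3.1 and 5.3.2 give different maximum numbers of participants to be dispensed: 73 and 70

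*Combined protocol and SAP*

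**What the plan says.** Section 5.3.1 derives 64 completers from a paired t-test and concludes that "up to 73 participants will be dispensed with study products with the goal to complete at least 64".

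Section 5.3.2 anticipates that "up to 73 potential participants may attend a Screening visit" and that "up to 70 participants may be randomized and dispensed with study products, with a target of at least 64 completing the study".

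Two other sections bear on what these counts mean. Section 5.1.2 states: "Participants will be randomized immediately prior to their first lens dispense". Section 5.5.1 states: "Participants will be assigned a unique alpha-numeric study ID after they sign the consent documentation", which is before eligibility has been confirmed. Section 14 lists what sites must report to the coordinating centre: "The number of participants screened, enrolled, and randomized (i.e. assigned a study ID number), discontinued and completed".

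No dropout rate or screen-failure rate is given anywhere in the document.

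**The concern.** The figure 73 is the dispensing maximum in one section and the screening maximum in the next, where the dispensing maximum becomes 70. Both sections are current text of version 1.5.

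Two things depend on which figure applies. The first is the enrolment limit. The 71st to 73rd participants dispensed would be within plan under 5.3.1 and beyond it under 5.3.2, so sites, the sponsor and the IRB are reading different limits. The second is how many participants can be lost after dispensing before the trial has fewer than the 64 completers it needs.

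**Working it through.** **Inputs.** From 5.3.1: mean paired difference 10, SD of paired differences 24.2, two-sided alpha 0.05, target power 90%, 64 completers, up to 73 dispensed. From 5.3.2: up to 73 screened, up to 70 randomised and dispensed, at least 64 completing.

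**Step 1: reproduce the plan's own figure.** Paired t-test power comes from the noncentral t distribution with n − 1 degrees of freedom and noncentrality (10/24.2) × √n.

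| n | Power stated in 5.3.1 | Power recomputed |
|---|---|---|
| 48 | 0.800662 | 0.800662 |
| 54 | 0.846406 | 0.846406 |
| 64 | 0.902344 | 0.902344 |

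The smallest n reaching 90% is 64 (n = 63 gives 0.8977). The sample size calculation is correct.

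**Step 2: check whether the two ceilings could refer to different things.**
- *Dispensed against randomised.* Section 5.1.2 places randomisation just before first dispense, so the two counts are essentially the same.
- *Dispensed against trial-fitted.* Lenses are fitted at Visit 0 and dispensed at Visits 1-0 and 2-0. Section 5.3.2 also uses the same term as 5.3.1 for the randomised group.
- *Both figures true at once.* If 73 is the screening maximum, dispensing 73 requires no screen failures. Section 5.3.2 itself leaves room for 73 − 70 = 3 (3/73 = 4.1%), and section 9 provides for screening failures.
- *Section 14.* It treats having a study ID as being randomised, but IDs are issued at consent. A status report using that definition could count screen failures as randomised, so it cannot show whether either ceiling has been reached.

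None of these reconciles the two figures.

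**Step 3: losses allowed after dispensing.**
- Under 5.3.1: 73 − 64 = 9, and 9/73 = 12.3%.
- Under 5.3.2: 70 − 64 = 6, and 6/70 = 8.6%.

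**Step 4: consequence for power.** This is conditional: the document gives no loss rate, and the table assumes that the ceiling is filled.

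| Losses after dispensing | Completers from 73 | Power | Completers from 70 | Power |
|---|---|---|---|---|
| 6 or fewer | 67 or more | above 90.2% | 64 or more | at least 90.2% |
| 7 | 66 | 91.1% | 63 | 89.8% |
| 8 | 65 | 90.7% | 62 | 89.3% |
| 9 | 64 | 90.2% | 61 | 88.8% |
| 10 or more | 63 or fewer | below 90% | 60 or fewer | below 90% |

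The ceilings lead to different conclusions only at 7, 8 or 9 losses. The largest shortfall against the plan's figure there is 90.2 − 88.8 = 1.4 points.

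**Step 5: what an assumed dropout rate would imply.** With d the assumed rate, 64/(1 − d), rounded up, gives 68 at 5%, 70 at 8%, 72 at 10%, 73 at 12% and 76 at 15%. Both 70 and 73 are therefore plausible, and only a stated rate would show which was intended.

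**The case against.** The strongest reply is that little turns on this. Both sections give the same operative target of at least 64 completers, the calculation behind it is right, and any dispensed total up to 70 satisfies both. Section 5.3.2 is worded as a forecast and 5.3.1 as a plan, and the examples of protocol deviations in section 15.4 do not mention exceeding an anticipated count. The power at stake is small and arises only within a narrow range of losses. The definition in section 14 is a side issue, and the allowances within 5.3.2 can be read off directly: 3 before dispensing and 6 after.

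Much of this stands as a statement of size. It is an inconsistency between sections, not an error in the power calculation, and no result is invalidated. It does not remove the contradiction: both sentences set an upper limit on the same count, and the limits differ. Reading the allowances off 5.3.2 presumes that 5.3.2 is the correct section, which the document does not establish. The section 14 point is secondary, and the main correction does not depend on it.

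One further point is fair. If 73 was the intended dispensing limit, changing 5.3.1 to 70 does have a price, because the loss margin falls from 9 to 6.

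**Conclusion.** The concern holds. The protocol gives two maxima, 73 and 70, for the number randomised and dispensed, and its text does not resolve them. The required 64 completers and 90.2% power are correct and unaffected. The difference is 3 participants in the enrolment ceiling and a post-dispense loss allowance of 9 (12.3%) or 6 (8.6%). The effect on power is at most about 1.4 points below 90.2%. That figure assumes a filled ceiling of 70, 7 to 9 losses, and the plan's own difference of 10 and SD of 24.2. The point should be corrected because the plan relies on this number, but it does not threaten the primary comparison.

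**What to change.** Use one screened number and one dispensed number in both sections. The choice is the sponsor's.

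- **Option A: 70 dispensed.** Amend 5.3.1 to up to 73 screened and up to 70 dispensed, aiming for at least 64 completers, and state that this tolerates at most 6 losses after dispensing (8.6%). This is a wording change with no added participants. The requirement of 64 completers and its 90.2% power stay as they are. If 73 had been the intended ceiling, the cost is 3 fewer losses that can be absorbed.
- **Option B: 73 dispensed.** Amend 5.3.2 to up to 73 randomised and dispensed, state that this tolerates at most 9 losses (12.3%), and set a screening number above 73. The cost is more screening visits than now anticipated and up to 3 more participants dispensed than 5.3.2 allows.

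Under either option, state the screen-failure and dropout numbers assumed. As a secondary tidy-up, section 14 should count participants as randomised at randomisation and not at ID assignment, so that status reports can be checked against the ceiling.
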